### 8.2.2. Change from Baseline in Platelet Counts

#### *Primary Analysis*

The primary Analysis will be performed on all observed data until Week 12, regardless of rescue medication and discontinuation.

Change from baseline in the average of the last 2 platelet counts will be analyzed using an analysis of covariance (ANCOVA) model with covariates including baseline platelets count, treatment, rescue medication use, and prior TPO-receptor agonist use.

The within-group least-square (LS) means, the associate standard errors (SE), and the treatment differences in LS means, the associated SE, 95% CIs and p-values will be derived from the model to compare each active treatment group against placebo.

Descriptive statistics of baseline value, observed value and change from baseline will be presented by treatment group.

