7.7.4 Analysis of Secondary Endpoints

For each binary endpoint (ie, definition of subject achieving 2 or more consecutive platelet counts), a logistic regression model will be performed and include treatment, baseline platelet count and prior TPO-receptor agonist use, provided there are enough subjects in each

subgroup. The odds ratio for the treatment effect compared to placebo (together with 95% CI and p-value) will be provided.

Time to platelet response will be estimated using the Kaplan-Meier method. Each active treatment group curve will be compared against placebo curve using log-rank test. In addition, a proportional hazard model will be implemented as well with treatment, baseline platelet count, and prior TPO-receptor agonist use.

Change from baseline in the average of the last 2 platelet counts will be analyzed using an analysis of covariance with baseline platelets count as covariate, treatment, and prior TPO-receptor agonist use. Each active treatment group will be compared with placebo.

Summary statistics of the following subjects will be provided by each treatment group:

- Subjects receiving rescue medication during the treatment period
- Subjects with Grade 2 or higher non-skin bleeding event during the treatment or follow-up period

A subject will be considered to have an event if the event was observed at least once during the treatment period or follow-up period as mentioned above.

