#### **4.4. Sample Size**

A minimum of 60 patients will be enrolled in the study. Patients will receive either 200 mg BID or 400 mg BID of SKI-O-703 or placebo in a 2:2:1 ratio.

Based on [Podolanczuk et al \(2009\)](#) at least 50% of patients in the active treatment group will be responders (R). A sample size of 24 patients per active treatment group and 12 patients in the placebo group will provide approximately 82.74% power to detect a difference between response rates of 50% and 1% in the active treatment and placebo groups, respectively, at the 2-sided 5% significance level. The test statistic used in the sample size calculation was the 2-sided Fisher's Exact test using the normal approximation method.

Patients that do not receive the study drug or do not provide at least 1 post baseline measurement will be excluded from the analysis above and replaced.

There will be no adjustment for multiple comparisons. The sample size calculation was performed using PASS 15 Power Analysis and Sample Size Software (2017). NCSS, LLC. Kaysville, Utah, USA, [ncss.com/software/pss](http://ncss.com/software/pss).

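### The ANCOVA of platelet change uses one residual variance for all arms, so the active-versus-placebo standard error is probably too wide, by roughly 5–50% depending on arm SDs the documents do not give.

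*SAP*

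**What the plan says.** In SAP 8.2.2 the change in the mean of the last two counts "will be analyzed using an analysis of covariance (ANCOVA) model with covariates including baseline platelets count, treatment, rescue medication use"; the model also adjusts for earlier TPO-receptor agonist use. The LS-mean differences, standard errors, 95% confidence intervals and p-values "will be derived from the model to compare each active treatment group against placebo". All observed counts to Week 12 are used, including those after rescue. Protocol 7.7.4 plans the same analysis without the rescue term: the endpoint "will be analyzed using an analysis of covariance with baseline platelets count as covariate, treatment, and prior TPO-receptor agonist use".

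Neither document provides for unequal variances, robust standard errors, a transformation or a rank analysis of this endpoint. The sensitivity analyses in SAP 8.2.2 change the handling of missing data and rescue, then refit the same ANCOVA.

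The planning figures are in SAP 4.4: "A sample size of 24 patients per active treatment group and 12 patients in the placebo group", and a "difference between response rates of 50% and 1% in the active treatment and placebo groups". No SD, effect size or power is stated for platelet change.

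**The concern.** With half of an active arm responding, its changes are a mixture of large gains and near-zero values. A placebo arm with 1% responders, all entering below 30,000/µL, is nearly homogeneous. One pooled variance, dominated by the 48 active patients, is then assigned to the 12 placebo patients, whose mean contributes most to the standard error when variances are equal. The reported standard error is therefore too large for active versus placebo.

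The pooling also links the doses. A very variable 400 mg arm inflates the error attached to 200 mg versus placebo, so the precision reported for one dose depends on the behaviour of the other. At stake are the width of the intervals and the chance of detecting a real effect on a secondary endpoint. None of the planned sensitivity analyses would reveal the problem.

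**Working it through.** **Inputs from the documents.** Arms of 24/24/12; response rates 50% and 1%; two-sided 5% (SAP 4.4). **Assumed, because not given:** the SD of platelet change in each arm. Platelet values below are in 10⁹/L.

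**1. The plan's own figure.** Pooled rate (12 + 0.12)/36 = 0.337. Null SE = √(0.337 × 0.663 × (1/24 + 1/12)) = 0.167. Alternative SE = √(0.25/24 + 0.0099/12) = 0.106. Continuity correction = 0.5 × (1/24 + 1/12) = 0.0625. Power = Φ((0.49 − 0.0625 − 1.96 × 0.167)/0.106) = 82.7%. The stated 82.74% reproduces. It belongs to the responder comparison and says nothing about the ANCOVA.

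**2. Model SE against true SE, covariates ignored.**
- Pooled variance: s² = (23·sA² + 23·sA² + 11·sP²)/57
- Model SE = √(s² × (1/24 + 1/12))
- True SE = √(sA²/24 + sP²/12)

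With r = sP/sA:

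| r | 0 | 0.2 | 0.37 | 0.5 | 0.7 | 1.0 | 1.25 |
|---|---|---|---|---|---|---|---|
| Model SE / true SE | 1.56 | 1.50 | 1.40 | 1.31 | 1.17 | 1.00 | 0.90 |

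**3. What the planning rates could imply for r.** For responder share p, responder gain D, and SDs sR (responders) and sN (non-responders), arm variance = p·sR² + (1−p)·sN² + p(1−p)·D². Take D = 40, sN = 10, sR = 30:
- Active (p = 0.5): 450 + 50 + 400 = 900, SD 30.
- Placebo (p = 0.01): 9 + 99 + 15.84 = 123.84, SD 11.1; r = 0.37.
- s² = (46 × 900 + 11 × 123.84)/57 = 750.2; model SE = √(750.2 × 0.125) = 9.68.
- True SE = √(37.5 + 10.32) = 6.92; ratio 1.40.

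Over D = 20–80, sN = 5–15 and sR up to 60, the ratio runs from 1.08 (D = 20, both SDs 15) to 1.51.

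**4. Power in that worked case.** True difference = 0.49 × 40 = 19.6. With the correct SE: Φ(19.6/6.92 − 1.96) = 81%. With the model SE the estimate must exceed 1.96 × 9.68 = 18.98, so power = Φ((19.6 − 18.98)/6.92) = 54%. Simulation without covariates (20,000 trials) gives 82% for Welch and 52% for the pooled test.

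**5. Simulation with covariates.** With baseline, prior TPO-agonist use and, where rescue was simulated, the rescue term, at 24/24/12 and 50% versus 1%, the ratio was 1.04–1.48. With responder median 80 and log-SD 0.6, power was about 53% pooled and 88% with HC3. With responder median 40, log-SD 0.3 and non-responder SD 15, almost no power was lost.

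**6. Rescue.** In the D = 40 case, suppose 10–30% of placebo patients have last counts raised by 20–60 and the model has no rescue term: the ratio is 0.95–1.32. With the planned rescue term, responder median 80, and half of rescued patients gaining a median of 40:
- Rescue in 20% of placebo and 10% of active non-responders: ratio 1.41–1.43, power about 39% pooled versus 76% HC3.
- Rescue in 40% and 20%: ratio 1.43–1.45, power about 25% versus 56%.

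**7. One dose inert.** Using step 3, give 200 mg and placebo variance 123.84 and 400 mg variance 900. Then s² = (34 × 123.84 + 23 × 900)/57 = 437.0. For 200 mg versus placebo, model SE = √(437.0 × 0.125) = 7.39 and true SE = √(123.84 × 0.125) = 3.93; ratio 1.88. In simulation the pooled test rejected 0.1% for the inert dose and Welch 4.7%.

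**8. Type I error.** With identical arms the pooled test rejected 4.8%. HC3 rejected 1–5% across null settings.

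**The case against.** The strongest objection is that the size cannot be read from the documents. A reader might infer a fixed inflation of about 40%. That needs a placebo-to-active SD ratio near 0.37, and no SD is stated. Only a range can be defended. This objection stands.

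Second, the 50% and 1% describe response at any visit without rescue, whereas the ANCOVA uses the last two counts regardless of rescue. Early transient responders may end low and rescued placebo patients may end high, so the planning rates suggest unequal variances but do not establish them. This also stands. The rescue part is weaker than it looks: with the planned rescue covariate, the inflation remained under the assumptions simulated.

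Third, a reader might infer that the p-values mislead towards false positives. They do not in these settings: the estimate is unaffected and the error is conservative. Nor does the point touch the Fisher test on the primary endpoint.

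Fourth, SAP 9.8 reuses this ANCOVA for SF-36, and a reader might extend the point there. The documents do not support that: a platelet responder mixture implies nothing about variances of quality-of-life scores, and none were examined.

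**Conclusion.** The point holds as a loss of efficiency on a secondary endpoint for which no power was planned. If active-arm changes vary more than placebo changes, the model standard error for each dose versus placebo is too wide: roughly 5–50% under the planning rates, with the position in that range set by SDs the documents do not give. The cost in power ranges from almost nothing to about 35 percentage points (88% − 53%). The precision for 200 mg also depends on how variable the 400 mg arm is.

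This rests on the any-visit rates being a fair guide to the mix in the last two counts, and on the assumed responder and non-responder distributions. If placebo were instead the more variable arm, the standard error would be too narrow (0.90 at r = 1.25), so the present model is not reliably conservative either. The primary analysis and the 82.74% power stand.

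**What to change.** Keep the raw-scale ANCOVA estimate in SAP 8.2.2. Before database lock, prespecify either arm-specific residual variances with Satterthwaite or Kenward-Roger degrees of freedom, or HC3 standard errors, for all comparisons of this endpoint. Apply the same choice within each imputed dataset of the treatment-policy and hypothetical-strategy repeats, so that the combined results use it too. A log-scale ANCOVA may be added as supportive; it is optional.

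The cost is SAP wording and some extra specification in the repeated models, with no new data. If the variances are in fact equal, slightly less efficiency is the price.

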#### *3.2.2.4. Others*

- Number of patients receiving rescue medication at least once during treatment period
- Patients with at least one Grade 2 or higher non-skin bleeding event during treatment period.

For each endpoint, a patient will be considered to have had an event if the event was observed at least once during the treatment period for rescue medication, and during treatment or follow-up period for bleeding event.

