## 7.2. Rescue Medications

In case of bleeding events requiring rescue medication, the following rescue medications are permitted: IVIG 1 g/kg/day for 2 days (ie, 2 g/kg), romiplostim 2 to 5 µg/kg, dexamethasone 40 mg/day for 4 days, other high dose parenteral steroids (ie, solumedrol 1 g IV), platelet transfusions (these may be reserved for serious or life threatening bleeding events), or standard of care as per participating countries. Patients should be withdrawn in case of CNS bleeding or life-threatening GI bleeding (see protocol Section 4.2.1).

Rescue medications will be coded to therapeutic drug classes (ATC level 2) and generic drug names using WHODD Enhanced B3 March 2018 or later. The number and percentages of patients who had any rescue medications will be summarized overall and by treatment, therapeutic drug classes (ATC level 2) and generic drug names based on ITT set. Therapeutic drug classes and generic drug names will be presented in a descending order of overall patient frequency, then the patient frequency within treatment groups from high dose to low dose and placebo group, if applicable.

A listing with all rescue medications will be generated.

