#### *Sensitivity Analysis based on treatment-policy strategy*

The primary analysis will be repeated based on assessments in all scheduled visits from post-baseline until Week 12, regardless of patients using rescue medication or discontinuation. The same MI method will be applied as outlined in [Section 8.1.2](#).

For each of m=25 imputed datasets, same ANCOVA model as defined in primary analysis will be carried out. Results from each of imputed datasets will be combined to generate the adjusted mean of change from baseline in platelet counts for each treatment group, as well as between-group difference (comparing each active treatment group against placebo) and the 95% CI for the difference.

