#### *Sensitivity analysis based on hypothetical strategy*

The primary analysis will be repeated based on a hypothetical scenario if the rescue medication had not occurred. Specifically, applying the same rescue medication window, all assessments happened within 28 days of the use of rescue medication will be considered as missing, regardless if they are collected or not. Then all missing data will be imputed until Week 12 by Multiple Imputation (MI) method for all treatment groups, under:

- Missing at random (MAR) framework:  
Under this framework, the same MI method will be applied as outlined in [Section 8.1.2](#).
- Missing not at random (MNAR) framework:

Two imputation steps will be performed under this assumption. First step for arbitrary missing is MCMC monotone imputation which is the same as described in Section 8.1.2. The second step is control-based pattern imputation using monotone regression method with seed 2010703, in which the missing data in all active treatment groups and placebo group will be imputed based on placebo group using the neighboring-case missing values method with k=2.

If model fail to converge because the number of visit is more than number of subjects, the same approach in [Section 8.1.2](#) will be applied. When imputed value out of range (ie value <0), the value will be replaced by min value in dataset.

The same ANCOVA model defined in primary analysis will be carried out to analyze the 25 complete datasets. The SAS procedure MIANALYZE will be used to combine the results for the statistical inferences

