## 9.8. Quality of Life as Measured by the SF-36 Score

The SF-36 Score consists of 8 scales: physical function scale, role physical scale, bodily pain scale, general health scale, vitality scale, social functioning scale, role emotional scale, and mental health scale. Scale scores range from 0 to 100, with higher scores indicating better health.

Three overall scores will be further derived: physical component summary, mental component summary, and health utility score (SF-6D). The SF-6D provides a single index for use in economic evaluation or for determination of quality adjusted life years, derived from seven of the eight scales in SF-36.

All 8 scale scores, 3 overall scores, and the answer to the Global Health questionnaire item (SF-36 question 1) will be summarized by scheduled visit. Change from baseline in scale scores, physical health summary measure, mental health summary measures, SF-6D, and the Global Health questionnaire item will be analyzed and reported using the same ANCOVA model as specified for change from baseline in platelet counts in [Section 8.2.2](#), using observed cases.

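### The SAP's change-from-baseline ANCOVA adjusts for rescue medication use, a post-randomisation outcome absent from the Protocol model, so it estimates neither the treatment-policy nor the no-rescue effect

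*SAP*

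**What the plan says.** Protocol 7.7.4 specifies, for this secondary endpoint, "an analysis of covariance with baseline platelets count as covariate, treatment, and prior TPO-receptor agonist use". SAP 8.2.2 (Primary Analysis) lists "covariates including baseline platelets count, treatment, rescue medication use, and prior TPO-receptor agonist use". The two differ only in the rescue term. The SAP does not say how the term is coded or why it was added.

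The same SAP paragraph bases the analysis on "all observed data until Week 12, regardless of rescue medication and discontinuation".

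On rescue itself, SAP 7.2 says: "In case of bleeding events requiring rescue medication, the following rescue medications are permitted". SAP 3.2.2.4 lists as a secondary endpoint: "Number of patients receiving rescue medication at least once during treatment period". Protocol 7.2.4 does the same.

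Three further analyses inherit the model:
- Treatment-policy sensitivity analysis (SAP 8.2.2): "same ANCOVA model as defined in primary analysis will be carried out".
- Hypothetical sensitivity analysis (SAP 8.2.2): "The same ANCOVA model defined in primary analysis will be carried out to analyze the 25 complete datasets".
- SF-36 (SAP 9.8): change from baseline is analysed "using the same ANCOVA model as specified for change from baseline in platelet counts in" section 8.2.2.

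SAP section 12 has one entry for 8.2.2. It concerns non-convergence and out-of-range imputed values, not covariates.

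**The concern.** A covariate in a randomised comparison should be fixed before treatment can affect it. Rescue use is not. A drug that raises platelet counts should reduce bleeding, and therefore rescue. Patients who are rescued also tend to be those with low counts. Comparing arms at equal rescue status therefore compares groups that treatment has already sorted, and part of the drug's effect is removed or distorted.

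The sensitivity analyses would normally expose such a problem. Here they carry the same term. The hypothetical analysis sets counts within 28 days of rescue to missing, imputes them, and then still adjusts for rescue. No model-based estimate of this endpoint omits the term; only the descriptive change-from-baseline summary does. The reported least-squares mean difference and its interval would have no clear meaning if the drug works, which is the case in which they would be used.

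**Working it through.** **Stated figures.** The plan gives no power, SD or effect for this endpoint. Its only power figure is 82.7% (SAP 82.74%) for the primary endpoint, 24 vs 12, 50% vs 1%. The pooled normal approximation with continuity correction reproduces it: (0.49 - 0.0625 - 1.96 x 0.1671)/0.1060 = 0.943, which is 82.7%. Nothing below changes that figure.

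**Algebra.** Let d be the reduction in the rescue proportion on active treatment, s the amount rescue adds to the final counts, and g the amount by which rescued patients' counts would have been lower without rescue, at the same treatment and baseline. Least squares gives:
- treatment-policy effect = no-rescue effect - d x s
- adjusted effect - treatment-policy effect = d x (s - g)
- adjusted effect - no-rescue effect = -d x g

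The adjusted effect does not depend on s. It equals the no-rescue effect only if d or g is zero, and the treatment-policy effect only if d is zero or s happens to equal g.

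**Large-sample check 1 (all inputs assumed).** Effect 20 x10^9/L, latent SD 15, residual SD 10, yes/no rescue triggered by a low noisy on-treatment count, 400,000 patients. Treatment-policy values are for rescue adding 0 / 10 / 30.

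| Rescue, active vs placebo | No-rescue effect | Treatment-policy | With rescue term |
|---|---|---|---|
| 2% vs 19% | 20.1 | 20.1 / 18.5 / 15.3 | 16.2 |
| 8% vs 36% | 20.1 | 20.1 / 17.2 / 11.5 | 13.5 |

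In the second row d = 0.36 - 0.08 = 0.28 and g = (20.1 - 13.5)/0.28 = 23.6. The formula then gives adjusted minus treatment-policy of 0.28 x (10 - 23.6) = -3.8 for s = 10 (simulated 13.5 - 17.2 = -3.7) and 0.28 x (30 - 23.6) = +1.8 for s = 30 (simulated +2.0). The small gaps are rounding.

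**Large-sample check 2 (all inputs assumed).** 48 scenarios: effect 20, SD 20, placebo rescue 8, 15, 30 or 45%, log-odds of rescue rising by 0, 0.5, 1 or 2 per SD lower count, rescue adding 0, 20 or 40.
- Adjusted minus treatment-policy: -6.6 to +4.3 (-5.2 to +3.3 if placebo rescue is at most 30%).
- Adjusted minus no-rescue: -6.6 to 0.
- Log-odds 0, so that rescue does not depend on counts or treatment: both differences are 0.
- Placebo rescue 30%, log-odds 1: treatment-policy 20.0 / 17.1 / 14.1 for rescue adding 0 / 20 / 40, against adjusted 17.4 / 17.5 / 17.5.

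Independent repeats of the ranges agreed to within 0.1.

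**Trial size, 24/24/12.** With no treatment effect, rejection is 4.5% to 5.8% with the term and 4.5% to 6.0% without it. With the check 1 mechanism (8% vs 36%) and rescue adding 10, the mean 400 mg vs placebo estimate is 17.0 (power 79%) without the term and 13.1 (power 52%) with it.

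**The case against.** **The change log.** SAP section 12 lists changes since SAP v0.2 and v1.0, so its silence does not prove that the term was a late addition, and Protocol 7.7 leaves analysis details to the SAP. That is right. What stands is narrower: no passage in either document records or explains the departure from Protocol 7.7.4.

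**The wording of 8.2.2.** The statement about observed data can be read as saying which data enter, not which effect is targeted, and Protocol 7.2.2 attaches no rescue rule to this endpoint. This softens the contradiction within the primary analysis. It does not help the two sensitivity analyses, which name their strategies and then condition on rescue.

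**Size.** The extremes need 45% placebo rescue. At 8% to 15% the shift from treatment-policy is -3.2 to +1.8, against a standard error of about 7 at 24/24/12, so at most 3.2/7 = 0.46 of a standard error. The simulations also omit rescue timing, the 28-day deletion and the imputation. These points limit how far the figures can be pressed. They do not make the adjusted estimate a valid estimate of either effect.

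**Precision.** With 30% placebo rescue, log-odds 1 and rescue adding 40, rejection is 46% without the term and 69% to 71% with it. Most of that gap is a change of target. With standard errors of 7.3 and 6.7 and a critical value of 2.00, a rough normal calculation gives 47% for 14.1/7.3, 54% for 14.1/6.7 and 73% for 17.5/6.7. Precision accounts for about 7 of those 26 points. When rescue adds nothing, deletion raises rejection from 70% to 78%.

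**Conclusion.** The concern holds. The SAP model conditions on a post-randomisation event that is itself a secondary endpoint, departs from Protocol 7.7.4 without a record or reason, and carries the term into both sensitivity analyses and SF-36. Whenever treatment changes rescue use and rescued patients would have had lower counts in any case, the adjusted difference falls short of the no-rescue effect. It may lie on either side of the treatment-policy effect, depending on how much rescue raises the counts. Neither the size nor the direction relative to treatment-policy can be fixed from the documents.

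The scope is one secondary endpoint and the exploratory SF-36 scores. The primary-endpoint logistic model in SAP 8.1.1 has no rescue term. This should be corrected, but it does not threaten the trial's main result.

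**What to change.** In SAP 8.2.2, Primary Analysis, delete rescue medication use, so that the model contains baseline platelet count, treatment and prior TPO-receptor agonist use, as in Protocol 7.7.4. The two sensitivity analyses and SAP 9.8 refer back to this model, so the correction carries through without further edits. Handling of rescue then rests with the treatment-policy and hypothetical strategies already planned.

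If the sponsor wants to keep a rescue-adjusted model, it should be a labelled supplementary analysis, with the departure from the Protocol stated and justified.

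The cost is one model term, with no new data or patients. Some precision may be lost if rescue raises counts strongly (standard error 7.3 instead of 6.7 in the scenario above).
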